##### **3.1.3 Secondary Aim:**

To identify changes in depression and anxiety from baseline to post treatment.

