### 6.2 Research Procedures

#### Baseline Assessment:

Once informed consent is obtained subjects will complete baseline measurements which include a demographics form, State-Trait Anxiety Inventory (STAI), and Edinburgh Postnatal Depression Scale (EPDS). An intrapartum form will also be completed via medical chart review.

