#### VR Assessment:

The VR intervention consists of three key hardware components required for use. 1) a plastic Virtual Reality Headset (also known as HMD: Head Mounted Display), which covers a user’s eyes and is secured to their head using elastic straps which can be tightened with Velcro. The HMD houses a 2) smartphone which runs the Flowly software and renders stereoscopic images which are presented to the user through the HMD. The phone connects to 3) a Bluetooth heart rate monitor which gathers heart rate data and clips simultaneously to the user’s ear lobe using a spring-loaded clip and to their clothing.

The subject will download an app to their smartphone that will transmit data to Amazon Web Services managed by Tamade, LLC. Subjects will be lent an iPhone if they do not have an iPhone or version that can support the VR sessions. In the case that subjects do have an iPhone 6s/6s+ or higher (iPhone 6/6+ not eligible), they will be asked to use it for the completion of the study.

Subjects will be given the mobile system VR Shinecon head mounted display (HMD) and Bluetooth sensors to provide patients Virtual Reality biofeedback sessions targeted for depression/anxiety. While the participant is using the VR intervention, the following outcome measure will be gathered: pain level, heart rate, and respiration will be taken via the device and smartphone app and stored in a database hosted by Amazon Web Services and managed by Tamade, LLC.

Subjects will then complete in a 1-hour VR session. In terms of the experience of the VANISH intervention, most exercises focus on breathing. Users will see objects in a 3D virtual world which change movements with their breathing and the user will be guided to use these in manners that manage body responses. Breathing resonance variation will be collected from the subjects during these exercises using the VR device. Training on how to complete these breathing exercises will be initiated as a part of the device-training.

Follow-up Assessment:

To conclude, a post-assessment STAI and EPDS will be repeated, as well as post-assessment feasibility questionnaire.

The subjects will participate in a total of 2-hours to complete all questionnaires and the VR session.

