## **7 Potential Risks and Benefits**

### **7.1 Reasonably Foreseeable Risks Related to Research**

*Risk associated with collecting and storing PHI.* Both common and infrequent risks include a loss of confidentiality.

*Risk associated with use of virtual reality devices.* No common risks are noted. Infrequent risks include the potential for patient to feel frustration, anxiety, or uncomfortable due to the device visualizations.

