## **10 Withdrawal of Subjects and Stopping Rules**

### **10.1 Adverse Events Requiring Discontinuation**

For this study, a serious adverse event is any untoward clinical event that is thought by either the investigator or the sponsor to be related to the study and results in any of the following outcomes:

1. Death
2. A life-threatening adverse event
3. Inpatient hospitalization or prolongation of an existing hospitalization
4. A persistent or significant incapacity or substantial disruption of the ability to conduct normal life functions.
5. A congenital anomaly or birth defect
6. Important medical events that may not result in death, be life threatening, or require hospitalization may be considered serious when, based upon appropriate medical judgment, they may jeopardize the patient, or subject, and may require medical, or surgical intervention to prevent one of the serious outcomes listed above.

If clinically important and unexpected adverse experiences or clinically important study-related adverse experiences occur, they will be recorded on the adverse event case report form.

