## **11 Statistical Analysis**

### **11.1 General Approach**

Baseline demographic characteristics will be collected and analyzed using descriptive statistics.

Feasibility of the study is measured as the number of patients who report that the study was both 1.) easy to use and 2.) The session was worth my time.

Acceptability was measured as “yes” responses to both questions, “would you participate in another session in the future? 2. Based on your experience today, would you participate in regular repeating sessions (e.g., daily, or weekly)?”

Anxiety and depression are measured as continuous variables at baseline and after VR intervention. Due to the small sample size, only the number (proportion) of patients whose overall anxiety and depression scores changed/decreased from baseline to post-intervention will be reported.

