#### **11.4 Analysis of Secondary Endpoint**

To further explore change in anxiety and depression across the trials.

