#### **12 Data and Safety Monitoring**

[name] will be responsible for data and safety monitoring. She will meet bi-weekly with study personnel to review the progress of the research study, including subject recruitment and retention and an assessment of the timeliness and quality of the data. [name] will review all data, procedures, and any adverse events that occurred. All adverse events, including breach of confidentiality, will be reported to the IRB at minimum at the time of renewal per their policies and procedures.

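### Section 11.1 does not commit to a count that shows how many women's anxiety or depression scores rose over the session

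*Combined protocol and SAP*

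**What the plan says.** The secondary aim in Section 3.1.3 is "To identify changes in depression and anxiety from baseline to post treatment". Section 11.4 restates it: "To further explore change in anxiety and depression across the trials". Neither names a direction or a summary statistic. Other places do have a direction: the study description in Section 1, the rationale in 2.2 and the primary analysis text in 11.3 all speak of reducing anxiety and depression.

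Under Section 6.2 both scales are completed at baseline, and after the session "a post-assessment STAI and EPDS will be repeated". Section 11.1 treats the two outcomes as continuous. It then gives the small sample as the reason for a restricted report: "only the number (proportion) of patients whose overall anxiety and depression scores changed/decreased from baseline to post-intervention will be reported". No other section plans a count of scores that rose or stayed the same, a mean or median change, or a listing of individual scores.

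Three other places bear on the point. Section 7.1 says of the device: "Infrequent risks include the potential for patient to feel frustration, anxiety, or uncomfortable due to the device visualizations". Section 11.2 expects the pilot to give estimates on the measured outcomes for the sample size of a later, fully powered trial. Section 1 records that 10 women were anticipated and 6 completed.

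**The concern.** *Changed* and *decreased* are different quantities, and the sentence joins them with a slash under a singular noun and the word *only*. Taken as one count, either choice hides the number of women whose scores went up. That number is relevant here. The participants have a diagnosed history of anxiety or depression, device-related anxiety is a listed risk, and STAI is the study's anxiety measure. A reader given one count would have only part of the answer to an aim about changes. Those planning the later trial would have neither the direction nor the size of change for each woman, although the study holds both.

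**Working it through.** The plan has no figure to reproduce: the sample is one of convenience, with no alpha, power or effect size. The check is whether the promised count determines the number of women whose score rose.

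**Inputs.** n = 6 completers (Section 1); one score per woman per scale before and after the session (6.2); the reporting rule in 11.1.

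**Possible results.** On one scale, let D, U and I be the numbers whose score decreased, was unchanged and increased, with D + U + I = 6. The number of possible splits is C(8,2) = 28.

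**Reading 1: one count, decreased.** Given D = k, I can be anything from 0 to 6 − k.
- I is fixed only at k = 6. That is 1 of the 7 possible reports, and 1 of the 28 splits.
- Example: 4 of 6 decreased fits I = 0 to 2, or 0% to 2/6 = 33.3%.
- The uncertainty comes entirely from ties. If U = 0, then I = 6 − k exactly. The reader would have to be told that U = 0, and the rule does not provide for that.

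**Reading 2: one count, changed.** Given D + I = m, I can be anything from 0 to m.
- I is fixed only at m = 0, again 1 of 7 reports and 1 of 28 splits.
- Example: 5 of 6 changed fits I = 0 to 5, or 0% to 5/6 = 83.3%.
- Here the absence of ties makes matters worse: m is then always 6, and I can be anything from 0 to 6.

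**Reading 3: both counts.** I = m − k, which is fixed in 28 of 28 splits. A three-way count does the same.

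**Other sample sizes.** The pattern does not depend on n = 6. For n = 5 (the number that 11.2 calls adequate), one count fixes I in 1 of 6 possible reports; for n = 10 (the number anticipated), in 1 of 11. With both counts, I is fixed in all 21 and all 66 splits respectively.

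These fractions count possibilities. They are not probabilities, because the splits are not equally likely and the documents give no results.

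**Precision with full reporting.** Exact (Clopper-Pearson) 95% limits:
- 0 of 6 worse: 0% to 1 − 0.025^(1/6) = 45.9%.
- 1 of 6 worse: 0.4% to 64.1%.

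The three-way count would therefore make the report complete, but not precise.

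**The case against.** The best defence is that the slash means two counts. That reading gives each word a purpose, and it closes the gap entirely. A lone count of changed scores would tell the authors little, so it is the least likely intention. This defence stands as far as intention goes. It does not settle the text, which nowhere commits to both counts.

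A second defence is that the study's stated purpose is reduction (Sections 1, 2.2 and 11.3), so a count of decreases is a coherent summary, and with continuous scores ties may be few. This also stands in part. It means that 3.1.3 cannot be said to require reporting in both directions; it only leaves direction open. But a test of reduction is still incomplete if no change and worsening cannot be told apart. A small sample is a reason to avoid tests, not to omit a tally.

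A reader might infer more than the documents support:
- *That worsening would go unnoticed.* The team holds the scores. Section 10.1 has a case report form for when "clinically important and unexpected adverse experiences or clinically important study-related adverse experiences occur", and under Section 12 the responsible person "will review all data, procedures, and any adverse events that occurred". Section 9.4.2 covers injuries. Safety routes exist, and a further investigator review of score increases would largely repeat Section 12.
- *That the wording was chosen to hide unfavourable results.* Version 2.0 does report that 6 women completed, but nothing shows that the choice of count was made after seeing scores.
- *That a rise would show harm from the device.* There is one arm and one session, and a small rise may be noise.

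**Conclusion.** The point holds as a minor, conditional defect of descriptive reporting. Unless both counts are given, the number of women whose scores rose is left undetermined except at one extreme result: all 6 decreased, or none changed. For the count of decreases, the loss also requires at least one tied score. The conclusion assumes the 6 completers as the denominator and a separate count for each scale. Section 11.1 does not say whether its overall scores are counted per scale or jointly, and a joint count would blur the picture further. The primary feasibility and acceptability measures are untouched. The stronger practical argument for a change may be Section 11.2: counts of direction, however complete, give no mean change or standard deviation for planning the later trial, whereas the individual scores would.

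**What to change.** Replace the sentence in Section 11.1 with one to this effect: for STAI and EPDS separately, among women with both scores, report the number and proportion whose score decreased, was unchanged and increased; give the number of consented women without a post-session score; and list each woman's pre and post scores under her study ID. State which STAI score is used, since the instrument's name covers both state and trait and the plan does not say.

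The denominator note is needed because the documents do not say how many women consented, and Section 10.2 allows withdrawal for incomplete survey data.

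The cost is one sentence, plus a tally and listing of 6 × 2 = 12 pre/post pairs, assuming one score per instrument. No new data or visits are needed. The listing should carry scores only, in keeping with the confidentiality terms in Section 8.1. The downside is that the summary may look less favourable, and a small rise may be over-read, so the text should say that changes are descriptive and not attributable to the device.

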### **11.2 Sample Size Determination**

This is a sample of convenience as a pilot trial. We believe five complete subjects' answers will give us adequate information about feasibility and some estimations on measured outcomes to perform a sample size calculation for the fully powered trial.

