### **11.3 Analysis of Primary Endpoint**

To explore the feasibility of use of Virtual Reality as a method to aid in the reduction of anxiety and depression in postpartum women.

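### The pilot is meant to supply estimates for sizing a full trial, but the planned reporting of EPDS and STAI gives only a count of women whose scores changed, with no size or spread of change

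*Combined protocol and SAP*

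**What the plan says.** All references are to the combined protocol and SAP.

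- **Purpose.** Section 11.2 describes a convenience sample for a pilot. It states the belief that five women with complete answers "will give us adequate information about feasibility and some estimations on measured outcomes to perform a sample size calculation" for the full trial.
- **Scale of the outcomes.** Section 11.1: "Anxiety and depression are measured as continuous variables at baseline and after VR intervention".
- **What is reported.** The same section gives the small sample as its reason and then sets the limit: "only the number (proportion) of patients whose overall anxiety and depression scores changed/decreased from baseline to post-intervention will be reported".
- **Secondary aim and analysis.** Section 3.1.3: "To identify changes in depression and anxiety from baseline to post treatment". Section 11.4 adds only: "To further explore change in anxiety and depression across the trials".
- **Primary measures.** In 11.1, "Feasibility of the study is measured as the number of patients who report that the study was both" easy to use and worth the time. Acceptability is a yes to two questions about taking part again. Section 11.3 gives a goal ("To explore the feasibility of use of Virtual Reality as a method") and no summary statistic.
- **Numbers of women.** Section 1 gives 10 anticipated and 6 completed.

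No section plans a mean change, an SD of change or a confidence interval, and none sets a success threshold.

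**The concern.** Sizing a trial on a continuous score needs the spread of that score and a view of the size of effect worth detecting. Section 11.2 looks to this pilot for estimates of that kind. The reporting rule in 11.1 reduces each woman's pre-post change to a yes or no, which discards its magnitude. The combined term changed/decreased also leaves open whether a woman whose score rose would be counted.

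Two things are at stake. First, a reader of the results could not see or check the SD behind a later sample size calculation, and would learn little about the secondary aim beyond a direction of change. Second, the feasibility and acceptability proportions would appear without any statement of their precision, although 11.2 describes the feasibility information from five women as adequate.

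**Working it through.** **The plan's own figure.** The five complete subjects in 11.2 cannot be reproduced by calculation. The plan gives no alpha, power, effect size, SD or precision target, and it calls the sample one of convenience. That is not an error; there is simply no calculation to check.

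**Inputs.** n=5 (section 11.2) and n=6 (section 1). The documents give no results, so every x/n and every change score below is hypothetical.

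**1. Does the count determine the spread?** Take two invented sets of six change scores:
- Set A: -1, -1, -1, -1, -1, +1. Five of six decreased. Mean = -4/6 = -0.67. Sum of squared deviations = 3.33. SD = sqrt(3.33/5) = 0.82.
- Set B: -12, -10, -8, -6, -2, +4. Five of six decreased. Mean = -34/6 = -5.67. Sum of squared deviations = 171.33. SD = sqrt(171.33/5) = 5.85.

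Under 11.1 both would be reported as 5/6. For a fixed target difference, required N is proportional to SD squared, so the two sets imply sample sizes in the ratio (171.33/5)/(3.33/5), about 51. The example is deliberately extreme. It shows only that the count leaves the SD open.

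**2. Precision of the primary proportions.** Exact (Clopper-Pearson) two-sided 95% limits. When x=n, the lower limit is 0.025^(1/n).
- 6/6: 0.025^(1/6) = 0.541, so 54.1-100%.
- 5/5: 0.025^(1/5) = 0.478, so 47.8-100%.
- From the beta quantiles, 5/6: 35.9-99.6%; 4/5: 28.4-99.5%.

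With five women, even a perfect result would not exclude a true proportion just below one half.

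**3. What reporting the mean and SD would deliver at n=6.**
- Half-width of the 95% CI for mean change: t(0.975, 5)/sqrt(6) = 2.571/2.449 = 1.05 SD.
- 95% limits on required N from uncertainty in the SD alone, df/chi-square with df=5: 5/12.83 = 0.39 and 5/0.831 = 6.0 times the computed N. This assumes normal change scores and a fixed target difference.

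The added summaries would therefore be informative but imprecise.

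**The case against.** A reader might infer that 11.1 and 11.2 contradict each other, so that the pilot cannot do what 11.2 asks of it. The documents do not support that. Section 11.1 limits what is reported, not what is collected. The investigators hold continuous scores before and after the session and can compute an SD for planning without publishing it.

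A reader might also infer that the plan withholds the one input the full trial needs. That goes too far as well, because the full trial's endpoint and design are not defined. A proportion could size a trial with a binary endpoint. Under normality, 5/6 decreased would even correspond to a mean fall of 0.97 SD, although 6/6 would give no finite value. But no binary endpoint is defined either, changed/decreased is ambiguous, and the interval around such a proportion would be as wide as those shown above.

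The limit in 11.1 is also deliberate. Mean changes from an uncontrolled single session in six women could be mistaken for evidence of efficacy. That caution stands, and it is why the added summaries need a descriptive label. It does not justify leaving them out.

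Finally, the width of the 6/6 interval might be read as a failure of the feasibility objective. It is not: 6/6 is a hypothetical best case, there is no threshold to miss, and any reader given x and n can work out the interval. A sampling interval for a convenience sample also has limited meaning.

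What remains is narrow. The plan names a use for the outcome estimates and then chooses a report that shows neither the size nor the spread of change, although both could be given at almost no cost.

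**Conclusion.** The point holds as a minor reporting mismatch. If the rule in 11.1 is followed, the published results will not contain the size or spread of EPDS and STAI change, although 11.2 names sizing a full trial as a use of the pilot's estimates and 3.1.3 aims to identify change. The missing intervals for feasibility and acceptability are a lesser part of the same point.

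No stated number is wrong, no decision rule is affected, and the investigators are not prevented from computing an SD. That a count does not determine an SD needs no distributional assumption. The 0.39 to 6.0 multipliers assume normal change scores and a fixed target difference, and the exact intervals treat the women as independent draws from a target population. The documents do not support a finding that the pilot is unfit for its purpose, or that the full trial must use a continuous endpoint.

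**What to change.** - **Sections 11.1 and 11.4.** Beside the planned proportions, report the mean and SD of EPDS change and of STAI change, with the individual values or 95% CIs. Label them descriptive and not evidence of efficacy. A note that an SD from six women is imprecise would be useful; the multipliers above could serve.
- **Sections 11.1 and 11.3.** Report feasibility and acceptability each as x/n with an exact (Clopper-Pearson) 95% CI.

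The justification in 11.2 need not be rewritten now that the study is complete, and this plan need not prescribe how a future trial, not yet designed, should handle uncertainty in the SD.

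The cost is a few lines of wording, two exact intervals and a small descriptive table from scores already collected. The downside is that the intervals will be wide and could be over-read, which the descriptive label is there to prevent.

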### **11.3 Analysis of Primary Endpoint**

To explore the feasibility of use of Virtual Reality as a method to aid in the reduction of anxiety and depression in postpartum women.

#### **11.4 Analysis of Secondary Endpoint**

To further explore change in anxiety and depression across the trials.

#### **12 Data and Safety Monitoring**

[name] will be responsible for data and safety monitoring. She will meet bi-weekly with study personnel to review the progress of the research study, including subject recruitment and retention and an assessment of the timeliness and quality of the data. [name] will review all data, procedures, and any adverse events that occurred. All adverse events, including breach of confidentiality, will be reported to the IRB at minimum at the time of renewal per their policies and procedures.

#### **13 Regulatory, Ethical, and Study Oversight**

##### **13.1 IRB Approval**

The PI obtained IRB approval **STUDY21040063**, from the University of Pittsburgh IRB, for the approval of the clinical protocol and corresponding informed consent form(s); modifications to the clinical protocol and corresponding informed consent forms, and advertisements (i.e., directed at potential research subjects) for study recruitment.

The only circumstance in which a deviation from the current IRB-approved clinical protocol/consent form(s) may be initiated in the absence of prospective IRB approval is to eliminate an apparent immediate hazard to the research subject(s). In such circumstances, the Investigator will promptly notify the University of Pittsburgh IRB of the deviation.

The IRB will review and approve the Informed Consent Document for the study and provide institutional oversight of data and safety issues. The study protocol will be approved prior to recruiting or obtaining consent from any participants. Moreover, the study will be reviewed at a minimum of annual basis (or more frequently as deemed necessary) by the IRB committee. Each participant will sign the approved Informed Consent Form prior to participating in the study.

The University of Pittsburgh IRB operates in compliance with FDA regulations at 21 CFR Parts 50 and 21 CFR 56, and in conformance with applicable ICH Guidelines on GCP.

